APPENDIX D – RETINAL EVALUATION SURVEY

Retinal Evaluation Survey (all subjects)

A. Please record any difficulty in performing retinal evaluation in each eye.

- 0 No difficulty
- 1 A little difficulty
- 2 Moderate difficulty
- 3 A lot of difficulty
- 4 Extreme difficulty

	Optic Disc		Macula		Mid-Periphery		Periphery	
BIO	OD	OS	OD	OS	OD	OS	OD	OS
0 - No difficulty								
1 - A little difficulty								
2 - Moderate difficulty								
3 - A lot of difficulty								
4 - Extreme difficulty								

SI E	Optic E	Disc	Macula	
SLE	OD	OS	OD	OS
0 - No difficulty				
1 - A little difficulty				
2 - Moderate difficulty				
3 - A lot of difficulty				
4 - Extreme difficulty				

B. Were you able to achieve stereoscopic view of the posterior pole?

Test	OD (Mar	k Yes/No)	OS (Mar	k Yes/No)
BIO	Yes	No	Yes	No
SLE	Yes	No	Yes	No

Comments:

SD-OCT & Fundus Photography Investigator Evaluation Survey (subgroup testing only)

A. Please grade image quality of the SD-OCT images

1- Excellent - No blurring or obstruction of retinal details

2- Adequate - Some blurring or obstruction of the retinal details

3- Inadequate - Marked blurring or obstruction of the retinal details

OCT	Optic	disc	Macula		
UC1	OD	OS	OD	OS	
1- Excellent					
2- Adequate					
3- Inadequate					

B. Please grade image quality of the fundus photos

Fundus Photos	 4 Wide Field (4W-D) or Modified 7 Standard Fields (7M-D) 	
	OD	OS
1- Excellent		
2- Adequate		
3- Inadequate		

APPENDIX E – RETINAL DIAGNOSTIC TESTING SUBGROUP INVESTIGATIONAL PLAN

The retinal diagnostic testing in the subgroup will follow the investigational plan and analysis plan specified below. Detailed methods and/or SOPs for training, analysis, reports will be provided by a reputable retinal image reading center.

SITE SELECTION

Three or four sites will be chosen based on the availability of the equipment necessary for conducting the testing.

QUALIFICATION OF THE SITES

Standardized testing methods from a retinal image reading center will be used for capturing images from dilated fundus exam and dilated OCT exam. One examiner and a potential backup examiner per site will be trained and certified by a retinal image reading center.

TRANSMISSION OF IMAGES

Images will be transmitted to the reading center's secure file sharing service. Image files (including raw image files) with all supporting documents should be exported from device to the reading center, but with all identifiable information redacted or masked. The files may be re-numbered or re-named for the purpose of masking.

GRADER(S) AT THE READING CENTER

The grader(s) at the reading center would be masked to the eye in which the investigational device has been implanted.

TIME POINT FOR DATA COLLECTION

Preoperative and 3-month postoperative visits.

DATA COLLECTION AND ANALYSIS

Image Quality

The grader would grade the quality of all images (SD-OCT and Fundus Photos) using the following grading scale or in accordance with the reading center's SOP:

- Excellent No blurring or obstruction of retinal details
- Adequate Some blurring or obstruction of the retinal details
- Inadequate Marked blurring or obstruction of the retinal details

SD-OCT Images

The standard macula and optic nerve images will be analyzed for the following variables:

1. Signal Strength

- 2. Retinal nerve fiber layer (RNFL) thickness
- 3. Segmentation- Retinal thickness and thickness of individual retinal layers

NOTE: If different OCT instruments are used to capture the images, software may be used to normalize the differences in measurements of the same variables from different instruments. This shall apply to raw image files supplied to the reading center and be conducted before image analysis is performed.

Fundus Photos

The following images will be captured and graded for image quality and presence of any artifacts: 4 Wide Field (4W-D) or Modified 7 Standard Fields (7M-D)

Visual Field (SITA Standard 30-2 Test)

Undilated visual field testing will be performed in the subgroup preoperatively and postoperatively at 3 months in both eyes. Detailed instructions will be given to the subject prior to testing. Visual field retests will be necessary for all false positives, false negatives and fixation losses > 33%. Repeat visual fields (at the 6 month postoperative visit) are necessary for results with anomalous outcomes as determined by the investigator.

The following variables will be captured and analyzed for visual field testing.

- 1) Fixation loss
- 2) False positives & negatives
- 3) Visual field assessment for abnormalities
- 4) Mean deviation
- 5) Pattern standard deviation

Number 1 to number 3 above may be analyzed by a reading center by way of evaluating the visual field test print-outs; numbers 4 and 5 above may be collected in the EDC system and analyzed by AcuFocus.

Planned Analysis

The following comparisons will be made for the variables collected:

- a. Between preoperative and 3-month postoperative visits
- b. Between eyes within subject at the 3-month postoperative visit

APPENDIX F – VISUAL ACUITY TESTING USING CTS

Distance, intermediate and near visual acuities will be measured using the ETDRS chart presented on a self-calibrating monitor on the CTS, at 4 m for all distance tests, at 66 cm for all intermediate tests and at 40 cm for all near tests. In a folded lane, the test distance is measured as the sum of the distances from the mirror to the subject and from the subject to the chart. CTS system monitor luminance can be automatically calibrated to 85 cd/m² and ambient room conditions (~5 lux per M&S CTS system) are measured with the integrated luminance photometer. These conditions will be established at each site study initiation visit and verified at least biannually by the Sponsor.

General Instructions

- The examiner should take precautions to remind the subject not to squint at any time during vision testing.
- Each presentation will be randomized to eliminate the memorization effect.
- The subject responds with the smallest line where all five letters can be correctly identified and the technician enters the line number and presses "Submit"
- The chart then randomizes, setting the selected line to the top line and a pointer is shown at the next smaller line
- The subject is then asked to read this line and the number of correct letters is entered; the pointer moves to the next line
- The test continues until the subject is no longer able to correctly identify any letters within a line
- When the test is complete the results are reported in the standard ETDRS Letter Score, Visual Acuity equivalent and logMAR equivalent

General Instructions for Infinity-Adjusted Vision Testing

• For each vision test, infinity-adjusted refraction must be used according to the instructions in **Table 7** (Section **9.7** in the study protocol).

For more detailed instructions refer to the CTS manual.

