9.7. POSTOPERATIVE PROCEDURES

Visual Acuity Testing:

Visual acuities will be measured using the ETDRS chart presented on a self-calibrating monitor in the M&S Clinical Trial Suite (CTS), at 4 meters for all distance vision tests, at 66 cm for all intermediate vision tests and at 40 cm for all near vision tests. CTS will automatically randomize the letter presentation to avoid memorization. **Table 6** shows the type of visual acuity measurement by eye and by visit. **Table 7** shows the infinity-adjusted refraction to be used for each visual acuity test. General instruction for all visual acuities tested using the CTS computerized vision testing system (M&S Technologies, Inc., Niles, IL, USA) is provided in **Appendix F**. Examiners should take precautions to remind subjects not to squint at any time during vision testing.

Uncorrected and Distance-Corrected Visual Acuities:

Monocular and binocular visual acuities with and without manifest refraction will be measured at distance, intermediate and near (**Table 6** and **Appendix A**).

NOTE: Best-corrected distance visual acuity (BCDVA) is same as Distance-corrected distance visual acuity (DCDVA).

Monocular and Binocular +0.75 D distance-corrected visual acuity (+0.75 DCVA):

+0.75 D distance-corrected visual acuity will be achieved by correcting all eyes in both groups with their distance-corrected refraction (plus infinity adjustment to refraction for each testing distance) and then placing a +0.75 D lens in front of the second eyes in both groups. Details on the refractions to be used for +0.75 D visual acuities are specified in **Table 7**.

Monocular and Binocular uncorrected and distance-corrected low contrast visual acuities (subgroup testing):

Low contrast visual acuity will be tested at distance, intermediate and near with 10% contrast. Measurements will be performed at the 6-month postoperative visit (and repeated at the 12month visit for those subjects that have had a posterior capsulotomy procedure after the 6-month visit) in the contrast sensitivity subgroup. The description of the contrast sensitivity subgroup is provided below under "Contrast Sensitivity Testing (subgroup testing)".

Visual Acuity	Illumination	Eye	Visit
Uncorrected distance visual acuity		Monocular	Day 1, Week 1, Months
(ICDVA)	Photopic		1, 3, 6, 12
(UCDVA)		Binocular	Months 3, 6, 12
Uncorrected visual acuity		Monocular	Months 3 6 12
intermediate (UCIVA) and near	Photopic	Binocular	Months 3, 6, 12

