(UCNVA)		Dinocular	Wommis 5, 0, 12
Distance-corrected distance visual		Monocular	Week 1, Month 1
acuity (DCDVA)	Photopic		
acuity (DCDVA)		Binocular	Months 3, 6, 12
Distance-corrected visual acuity		Monocular	Months 3, 6, 12
intermediate (DCIVA) and near	Photopic		
(DCNVA)		Binocular	Months 3, 6, 12

 Table 6: Visual Acuity Measurements

+0.75 D distance-corrected visual		2 nd Eye	Month 6
intermediate (+0.75 DCIVA) and near (+0.75 DCNVA)	Photopic	Binocular	Month 6
Low contrast UCDVA, UCIVA, UCNVA, DCDVA, DCIVA,		2 nd Eye	Month 6
DCNVA (10%) (contrast sensitivity subgroup only)	Photopic	Binocular	Month 6

Manifest Refraction:

Manifest refraction should be measured using the CTS at 13 feet or 4 m. Because of the extended depth of focus provided by the small-aperture optics, determination of the refractive endpoint in IC-8 IOL eyes may potentially be challenging when patients can tolerate a wider range of refractive error without necessarily exhibiting a noticeable drop in visual acuity, and the manifest refraction measurement could have a "fuzzy" endpoint. Taking this into consideration, determination of the middle point of the emmetropic range of the depth of focus should be best accomplished by using the duochrome technique. The duochrome test is less likely to be influenced by the extended depth of focus because it is based on the principle of chromatic aberration. Therefore, manifest refraction should be determined using the duochrome technique (commonly known as the red/green test) postoperatively. To maintain examiner masking and avoid bias between groups, manifest refraction should be measured at all postoperative visits beyond Day 1. Instructions for performing manifest refraction with the red/green test using the CTS are provided in **Appendix G**.

Infinity-Adjusted Refraction for Vision Testing:

Postoperative manifest refractions for the study are to be performed using the ETDRS charts at 4 m using the CTS. Because 4 m is not optical infinity, adjustments to the manifest refraction are necessary for visual acuity tests taking into account the vision test distances (4 m for distance vision tests, 66 cm for intermediate vision tests, and 40 cm for near vision tests) and the refraction distance (4 m). **Table 7** lists the infinity-adjusted refraction to be used for each vision test in the study when using the 4 m refraction.

Vision Test	Infinity-Adjusted Refraction
UCDVA	+0.25 D
UCIVA	None
UCNVA	None
DCDVA	Manifest Refraction

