 - a. The mean acuity from the test group is non-inferior to the mean acuity from the control group using a margin of 0.1 logMAR. The comparison between test and control groups for mean binocular UCDVA (logMAR) will be performed using a t-test for non-inferiority at $\alpha = 0.05$ (one-sided). The null hypothesis is that the mean acuity for the test group is inferior to the control group by 0.1 logMAR or more. The alternative hypothesis is that the mean acuity for the test group by less than 0.1 logMAR. Formally put as follows:

$$\begin{split} &H_0{:}\,\mu_T-\mu_C\geq 0.1\\ &H_A{:}\,\mu_T-\mu_C<0.1 \end{split}$$

Where μ_T is the mean logMAR acuity from the IC-8 test group and μ_C is the mean logMAR acuity from the control group.

The statistical success criterion is when H_0 is rejected by a p-value less than 0.05, demonstrating the mean binocular UCDVA from the test group is statistically non-inferior to the mean binocular UCDVA from the control group using a margin of 0.1 logMAR.

- b. At least 50% of test subjects achieve 0.1 or better logMAR [clinical success criteria].
- 4. Monocular distance-corrected intermediate visual acuity (DCIVA) of the IC-8 IOL eyes (at 6 months):
 - a. The mean acuity of the IC-8 IOL eyes is statistically superior to the fellow control eyes in the test group. The comparison between IC-8 IOL eyes and fellow eyes in the test group for mean monocular DCIVA (logMAR) will be performed using a two-sample t-test at $\alpha = 0.05$ (two-sided). The null hypothesis is that the mean acuity for the IC-8 IOL eyes is greater (i.e., worse) than or equal to that for the fellow eyes. The alternative hypothesis is that the mean for the IC-8 IOL eyes is less (i.e., better) than that for the fellow eyes. Formally put as follows:

$$H_0: \mu_T \ge \mu_C$$
$$H_A: \mu_T < \mu_C$$

Where μ_T is the mean logMAR acuity from the IC-8 eyes and μ_C is the mean acuity from the fellow eyes.

The statistical success criterion is when H_0 is rejected by a p-value less than 0.05, demonstrating the mean DCIVA from IC-8 eyes is statistically superior to the mean DCIVA from the control eyes.

- b. At least 50% of IC-8 IOL eyes should achieve DCIVA of logMAR 0.2 or better [clinical success criteria].
- 5. Monocular photopic distance-corrected depth of defocus (measure only negative direction from zero) of the IC-8 IOL eyes (at 3 months):

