APPENDIX H – DEFOCUS CURVE TESTING

Defocus curve testing will be done using the CTS computerized testing system. For detailed instructions refer to CTS user manual. The laptop will show the test, distance, light level and the correction needed for the testing.

Defocus curves will be performed monocularly and binocularly using ETDRS charts in the CTS calibrated for 4-meter test distance in standard photopic conditions, with the best-corrected distance manifest refraction.

A defocus curve should be obtained by using the manifest refraction and measuring the visual acuity between +2.00 D and -5.00 D in 0.5 D defocus steps, except in the region from +0.50 D through -0.50 D, which should be done in 0.25 D steps. The examiner will progressively change the defocus in 0.50 D steps from +2.00 D to +0.50 D, then in 0.25 D steps from +0.50 D to -0.50 D, then in 0.50 D steps from -0.50 D to -5.00 D, while measuring visual acuity at each successive defocus step. No infinity adjustment to refraction is needed for defocus curve testing. Letters will be randomly presented to avoid memorization by CTS automatically.

The test heading on the laptop and the tablet will indicate which lens to use. With the lens in place the tester will begin the vision testing. The tablet will display all lines from 20/200 to 20/10.

General Instructions:

- The examiner should take precautions to remind the subject not to squint at any time during vision testing.
- Each presentation is automatically randomized to eliminate the memorization effect.
- The subject responds with the smallest line where all five letters can be correctly identified and the technician enters the line number and presses "Submit"
- The chart then randomizes, setting the selected line to the top line and a pointer is shown at the next smaller line
- The subject is then asked to read this line and the number of correct letters is entered; the pointer moves to the next line
- The test continues until the subject is no longer able to correctly identify any letters within a line
- When the test is complete the results are reported in the standard ETDRS Letter Score, Visual Acuity equivalent and logMAR equivalent

For more detailed instructions refer to the CTS manual.

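### Appendix F builds the folded-lane test distance from the wrong path segment, so a lane set to 4 m by its text need not be an optical 4 m

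*Combined protocol and SAP*

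**What the plan says.** Appendix F places acuity testing "at 4 m for all distance tests, at 66 cm for all intermediate tests and at 40 cm for all near tests", and Section 9.7 repeats the 4 m requirement ("at 4 meters for all distance vision tests"). For a lane folded by a mirror, Appendix F states that "the test distance is measured as the sum of the distances from the mirror to the subject and from the subject to the chart". The protocol gives no other folded-lane formula; for further detail Appendix F refers to the CTS manual.

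Other procedures rely on the 4 m being a real optical distance:

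- **Refraction** (Section 9.7): "Manifest refraction should be measured using the CTS at 13 feet or 4 m".
- **Table 7 adjustments** (Section 9.7): "Because 4 m is not optical infinity, adjustments to the manifest refraction are necessary for visual acuity tests".
- **Defocus curve** (Appendix H): "calibrated for 4-meter test distance in standard photopic conditions".

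On site checks, directly after the sentence on luminance and room lighting, Appendix F says: "These conditions will be established at each site study initiation visit and verified at least biannually by the Sponsor".

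**The concern.** In a mirrored lane the eye sees the chart's reflection. The viewing distance is therefore chart to mirror plus mirror to eye. The Appendix F sum drops the chart-to-mirror leg and replaces it with the direct distance between subject and chart, which the light does not travel.

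A lane laid out by this sentence can be longer or shorter than 4 m. Letters sized for 4 m then subtend the wrong angle, and every distance acuity recorded in that lane moves by a fixed amount. The results exposed are those judged against a fixed cut-off:

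- first-eye qualification at UCDVA 20/32 and BCDVA 20/25 (Section 7.3), which decides who stays in the study;
- the co-primary UCDVA criterion, "At least 50% of test subjects achieve 0.1 or better logMAR" (Section 18.2.1, item 3b);
- BCDVA of 0.3 logMAR or better, set against 92.5% and 96.7% (Section 18.3.1);
- the BCDVA 20/25 condition for the mITT set of the secondary endpoint (Sections 18.1 and 18.2.2);
- the 0.2 logMAR crossing that defines depth of focus (Section 18.2.1, item 5).

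A mixture of straight and wrongly measured folded lanes across 18 to 25 sites would also add variability between sites.

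**Working it through.** **Inputs from the protocol.** The folded-lane rule and the 4 m distance (Appendix F); the 0.25 D adjustments (Table 7); 0.12 logMAR taken as 6 letters, so 0.02 logMAR per letter (Section 18.2.2).

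**Assumed, because the protocol gives no lane dimensions.** The position of the chart and the subject-to-mirror distance.

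**Step 1: the plan's own use of 4 m.** The vergence at 4 m is 1/4 = 0.25 D, the size of the Table 7 adjustments. The 4 m is therefore meant as an optical distance.

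**Step 2: geometry.** Let a = mirror to subject, c = subject to chart, b = mirror to chart.

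- Rule as written: a + c = 4.
- True path: d = a + b = 4 + (b − c).
- So d = 4 only if b = c. On the lane axis that means a chart midway between subject and mirror (a = 2.67 m, c = 1.33 m); off the axis, other positions also satisfy it.

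**Step 3: acuity shift.** Recorded minus true logMAR = log10(d/4). A positive value means acuity is recorded too poor.

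*Chart level with or behind the subject:* b = a + c = 4, so d = 4 + a.

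| a (m) | c (m) | d (m) | shift (logMAR) | letters | 0.25 − 1/d (D) |
|---|---|---|---|---|---|
| 0.5 | 3.5 | 4.5 | +0.051 | 2.6 | 0.028 |
| 1 | 3 | 5 | +0.097 | 4.8 | 0.050 |
| 2 | 2 | 6 | +0.176 | 8.8 | 0.083 |
| 3 | 1 | 7 | +0.243 | 12.2 | 0.107 |
| 4 | 0 | 8 | +0.301 | 15.1 | 0.125 |

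*Chart to the side of the subject at 90°:* b = √(a² + c²). For a = 1, 2, 3 m: d = 4.16, 4.83, 6.16 m; shift +0.017, +0.082, +0.188.

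*Chart between subject and mirror:* b = a − c, so d = 2a − c = 3a − 4. For a = 2.33, 2.67, 3 m: d = 2.99, 4.00, 5.00 m; shift −0.126, 0, +0.097. Below a = 2.67 m the path is under 4 m and acuity is recorded too good.

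**Step 4: effect at a cut-off.** 20/25 is log10(25/20) = 0.097 logMAR. At a true 6 m, an eye with BCDVA of 0.0 would be recorded at about 0.18 and would fail first-eye qualification.

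**Step 5: effect on a difference between arms.** A fixed lane error s applies to both arms at a site. The bias in the arm difference is s multiplied by the difference between arms in the share of affected subjects. A bias of 0.1 logMAR would need a difference in shares of 0.1/0.301 = 0.33 at 8 m. At 5 m it would need 0.1/0.097 = 1.03, which is impossible. Section 7.0 expects about 15 test and 5 control subjects at each site, so both arms should meet the same lanes in similar proportion.

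**The case against.** The strongest reply is that exposure is not shown. No section says that any site uses a folded lane, the Appendix B equipment list contains no mirror, and straight lanes are unaffected. The 4 m requirement itself is stated correctly and repeatedly, and the CTS manual or the sponsor's set-up may lead sites to the right measurement despite the sentence. All of this stands as a limit on likely impact. None of it makes the sentence correct.

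Four stronger readings are tempting, and the documents do not support them.

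- **That 5 to 8 m is what sites would have.** The range depends on an assumed layout. The 8 m end puts the subject 4 m from the mirror with the chart alongside, and a room of that length would hardly need folding. Nor is 5 m a floor: 4.5 m and 4.16 m also satisfy the rule.
- **That acuity always reads too poor.** With the chart between subject and mirror the sign can reverse. Where the path is too long, the error makes the acuity criteria harder to meet and would not create a false success on them. Where it is too short, it makes them easier.
- **That the error uses up the 0.1 logMAR non-inferiority margins.** Those margins apply to differences between arms (UCDVA) or between eyes of the same subjects (BCDVA), where a site-wide shift largely cancels (Step 5). DCIVA is measured at 66 cm, not in the 4 m lane.
- **That the sponsor's checks would repeat the error.** The conditions to be verified follow the luminance sentence and may not include lane length. If they do include it, checking against this text could confirm a wrong lane, but that is not established.

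The knock-on to refraction is small: 0.05 to 0.125 D at 5 to 8 m, at most half of the 0.25 D refraction step.

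**Conclusion.** The point holds as an error in an operative instruction. The folded-lane sentence in Appendix F omits the mirror-to-chart leg, and it returns a true 4 m only when the subject-to-chart and mirror-to-chart distances are equal. That follows from geometry and needs no assumption.

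The size does rest on assumptions. With the chart level with or behind the subject and the subject 1 to 4 m from the mirror, the shift is 0.10 to 0.30 logMAR towards poorer acuity. Other layouts give less, or the opposite sign. The number of folded-lane sites is unknown and may be zero.

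The consequence lies in the absolute thresholds listed above and in between-site variability, not in the mean comparisons. Depth of focus is an intermediate case. It compares two eyes of one subject, but a common shift moves the 0.2 logMAR crossing along two curves of different shape, so the 0.5 D difference between eyes need not be preserved. The sentence should be corrected; nothing here shows that the trial's comparative conclusions would be wrong.

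**What to change.** Replace the Appendix F sentence with: *In a folded lane, the test distance is the sum of the distances from the chart to the mirror and from the mirror to the subject's eye.*

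State that lane length is among the conditions checked. Record for each site whether the lane is straight or folded, and the measured path, at the initiation visit and at the biannual verifications. If a lane has already been set by the present wording, the recorded path allows the shift log10(d/4) to be calculated for that site and used in a sensitivity analysis of the threshold criteria.

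The cost is one sentence, one field on the site checklist, and a tape measurement at visits already planned.
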